#### **9.5. Concomitant Procedures**

A listing will be provided for concomitant procedures the subject underwent during the study. No other analysis is planned for concomitant procedures.

This document is confidential.

## 10. Efficacy

All efficacy analyses will be performed on the ITT population, unless otherwise specified.

### 10.1 Handling Rules for sUA Values

Serum samples for measurement of sUA levels are scheduled for collection at the Screening Visit (Within 35 Days of the Day 1 Visit), and prior to and after the end of each pegloticase infusion before discharge from the Pegloticase Treatment Period. Additional serum samples for sUA levels are collected at non-infusion Visits at Weeks 21 and 23 and the End of Pegloticase Infusions Visit (if applicable), the Week 24/End-of-Study/Early Termination Visit, and the 3-month Follow-up Visit. Subjects with a pre-infusion sUA level >6 mg/dL at 2 consecutive study visits beginning with the Week 2 Visit will discontinue pegloticase and complete the End of Pegloticase Infusions Visit (if applicable) or the Week 24/End of study/Early Termination Visit procedures.

- For the determination of sUA responder endpoints, scheduled assessments of sUA and unscheduled assessments of sUA, reported by the central laboratory, will be used. Local laboratory-processed pre-infusion sUA results will be used at a visit only when the central laboratory-processed value at a time point is not available, but the local lab-processed pre-infusion value, collected value at the same time point, is available.
- When the central laboratory or local laboratory reports a value for sUA as being lower than the lab assay's limit of quantification (e.g. "<0.02"), zero will be used as the numeric value for the purpose of determining response and for summaries of observed values and the change from baseline.

### 10.2 Primary Efficacy Endpoint and Analysis

The primary efficacy endpoint is the proportion of Month 6 (Weeks 20, 21, 22, 23 and 24) responders, defined as subjects achieving and maintaining sUA <6 mg/dL for at least 80% of the time during Month 6.

The sUA concentrations vs. time (collected to the nearest minute in the CRF) curve will be used to estimate the proportion of time that the sUA is < 6 mg/dl using the available pre-infusion, non-infusion (if available), and post-infusion samples with non-missing sUA values.

The Month 6 period will include pre-infusion and post-infusion results at Week 20, results at Week 21, pre-infusion and post-infusion results at Week 22, results at Week 23, and results at Week 24 processed by the central laboratory. Central laboratory results from visits at which an infusion was not performed (e.g. subject discontinued pegloticase but remained in study or unscheduled visits) will be used when available. Section 10.1 shows the rules for inclusion of sUA values reported by local laboratories.

There will be no imputation of sUA values due to missed collections among those collected between Week 20 and Week 24. Only observed values will be included in the calculation. If central lab results are available, central lab results are used. If central lab results aren't available, local lab results will be used.

This document is confidential.

[REDACTED]

[REDACTED]

[REDACTED]

[REDACTED]

Results from visits where an infusion was not performed (e.g. subject discontinued pegloticase but remained in study) will be used when available. The only exception to this approach is for subjects meeting the stopping rule. Subjects meeting the stopping rule prior to Week 24 will be counted as non-responders. If only one sUA result is collected during the Month 6 period, response will be based on the single value being strictly < 6 mg/dL.

For subjects who postponed or missed visits due to COVID-19, only visits occurring prior to any disruption of treatment (> 21 days between infusions) or cessation in treatment will be used for the primary analysis. Any results following the disruption in treatment will be set to missing. Subjects with disrupted treatment due to COVID-19 at any point prior to the Month 6 period will not be included in the primary analysis.

The proportion of hours during the period during which the sUA was less than 6 mg/dL will be summarized using descriptive statistics. If a subject has  $\leq 1$  data point in the period, then the proportion of hours will not be calculated. The number and proportion of subjects that discontinued treatment due to the stopping rule will be summarized. The number and proportion of responders will be summarized along with a 95% exact (Clopper-Pearson) CI for the proportion. In addition, the number and proportion of subjects missing all data in analysis period, subjects with only one measurement (above cutoff) in analysis period, and subjects with only one measurement (below cutoff) in analysis period will be summarized.

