Study Design: This is a Phase 4, multi-site, open-label, efficacy and safety study of pegloticase in adult subjects with uncontrolled gout who have undergone kidney transplantation. Twenty subjects will be enrolled. The study design will include: 1) a Screening Period, lasting up to 35 days; 2) a 24-week treatment period which includes an End-of-Study (Week 24)/Early Termination Visit; 3) a safety follow-up phone/email Visit 30 days after the last infusion; and 4) a 3-month post-treatment follow up visit. During the Screening Period, eligibility will be confirmed. Samples for measurement of sUA levels will be collected at the Screening Visit, prior to each infusion, 15-60	

minutes after the end of each infusion and at the End-of-Study/Early Termination Visit. Additional samples for sUA levels will be collected at non-infusion Visits at Weeks 21 and 23.

Subjects who meet all of the inclusion criteria and none of the exclusion criteria during Screening will be enrolled at the Day 1 Visit to receive pegloticase 8 mg administered IV every 2 weeks from Day 1 through Week 22, inclusive. During this 24-week treatment phase, subjects who meet the stopping rule (pre-dose sUA level >6 mg/dL at 2 consecutive study visits beginning with the Week 2 Visit, see Stopping Rule section below) or discontinue treatment for any other reason will complete the End-of-Pegloticase-Infusions Visit procedures within 2 weeks and be encouraged to continue to participate in all visits through the end of the study. Subjects will return for regularly scheduled visits and will complete all study visit procedures with the exception of the pegloticase infusion and IR prophylaxis. After the Week 24 Visit (or End-of-Pegloticase-Infusions Visit [if applicable]), subjects should resume regular care for gout per the judgment of the treating physician, including resumption of urate-lowering therapy (ULT) upon pegloticase discontinuation, if appropriate. Subjects will have a 3-Month Follow-up visit to assess clinical status, including sUA levels.

On days of scheduled infusions, pegloticase will be administered after all pre-dose visit assessments have been completed. The date and start and stop time of infusion will be recorded. The date of the first dose of pegloticase is defined as Day 1. All subsequent doses and study visits will be scheduled based on the Day 1 visit date.

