#### **Criteria for Evaluation:**

Efficacy will be assessed by sUA levels, tophus resolution, tophus size, urate deposition volume and bone erosion due to gout (determined by DECT), BP, and physician global assessment of gout.

Quality of life will be assessed using the Health Assessment Questionnaire - Disability Index (HAQ-DI),

■  
Pharmacokinetic and Anti-drug Antibody Endpoints:

- Serum concentrations of pegloticase; and
- Profile of anti-PEG and anti-uricase IgG antibodies.

Safety Endpoints:

The safety endpoints include the following:

- Overall AE/SAE profile;
  - Incidences of AESI: IRs, anaphylaxis, gout flares, cardiovascular events;
- Laboratory tests;
- Vital signs and physical examination; and
- Incidence of renal rejection (biopsy proven).

Statistical Analysis of Efficacy Parameters

The efficacy analysis will be performed using the modified intention-to-treat (mITT) population, defined as all enrolled subjects who received at least 1 dose of pegloticase. The proportion of Month 6 responders will be summarized, along with a 95% confidence interval (CI) for the proportion. The proportion of 5 mg/dL responders during Month 6 will be analyzed similarly.

A subject will be declared a non-responder if the subject had sUA level >6 mg/dL at 2 consecutive study visits beginning with the Week 2 Visit through Week 24 (for the primary endpoint) and through Week 14 (for exploratory endpoints). In addition, a subject who withdraws from study treatment for any reason after the first dose of pegloticase and prior to Month 6 (for the primary endpoint) or Month 3 (for exploratory endpoints) will be considered a non-responder if sUA values are not collected at the planned time points.

The proportion of subjects with resolution of  $\geq 1$  tophus (100% decrease in the area of at least 1 tophus) at Week 24 will be summarized along with the corresponding 95% CI. HAQ scores (Disability Index [DI], pain, and health), sUA, urate volume, tophi size, bone erosion, SBP, DBP, MAP, physician global assessment, eGFR, and UACR will be summarized at each visit with descriptive statistics. Changes from baseline will be summarized along with 95% CIs.

Special consideration may be given to subjects who discontinue the study or miss visits due to reasons related to the COVID-19 pandemic.

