##### 9.6.5.1 Primary and Secondary Endpoint Analysis

The primary efficacy endpoint is the proportion of responders during Month 6. A responder is defined as a subject for whom the proportion of time that the sUA-time curve is  $<6$  mg/dL during the analysis interval is at least 80%. The proportion of time that the sUA level is below 6 mg/dL is defined as the ratio of the time during which the sUA level remains below 6 mg/dL (using linear interpolation, if necessary) to the entire time interval during Month 6. The proportion of responders will be summarized, along with a 95% exact (Clopper-Pearson) confidence interval (CI) for the proportion.

A subject will be declared a non-responder if the subject had 2 pre-infusion sUA levels  $>6$  mg/dL at 2 consecutive study visits beginning with the Week 2 Visit and prior to or during Month 6. Additionally, a subject who withdraws from study treatment for any reason other than the stopping rule after the first dose of pegloticase and prior to or during Month 6 will be considered a non-responder if sUA values are not collected at planned timepoints. Special consideration may be given to subjects who discontinue the study or miss visits due to reasons related to the COVID-19 pandemic.

The mean change from baseline to each visit in HAQ pain score and HAQ-DI score will be summarized with descriptive statistics, including 95% CIs for the change from baseline.

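### Month 6 sUA taken on restarted oral urate-lowering therapy can count as pegloticase response in subjects who stop early for reasons other than the stopping rule or COVID-19

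*SAP*

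**What the plan says.** **Scoring.** SAP 10.2 builds Month 6 response from the sUA values at Weeks 20 to 24. For subjects off infusions it states: "Results from visits where an infusion was not performed (e.g. subject discontinued pegloticase but remained in study) will be used when available". Subjects who meet the stopping rule are failed. After a COVID-19 disruption, "Any results following the disruption in treatment will be set to missing". If only one Month 6 value exists, "response will be based on the single value being strictly < 6 mg/dL". SAP 10.3.1 applies the same method to the <5 mg/dL endpoint.

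**Protocol counterpart.** Under protocol 9.6.5.1, a subject who leaves treatment for a reason other than the stopping rule "will be considered a non-responder if sUA values are not collected at planned timepoints". If the values are collected, they are scored.

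**When ULT may restart.** The synopsis says: "After the Week 24 Visit (or End-of-Pegloticase-Infusions Visit [if applicable]), subjects should resume regular care for gout per the judgment of the treating physician". Protocol 9.1 and SAP 4.1 say the same in substance. Protocol 9.3.3.1.1 and 9.4.10 hold oral ULT back only until the End-of-Pegloticase labs are collected, and footnote 3 of the Schedule of Assessments places that visit within 2 weeks of the last infusion. Protocol 9.3.3.1.1 also urges early stoppers to attend Weeks 20 to 24 so that sUA is measured.

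**What the visible text does with ULT.** SAP 9.4.2 tabulates gout medications started after the last infusion but does not link them to response. Sensitivity analysis (1) adds post-stop values of stopping-rule subjects without regard to ULT. The treatment-status split in SAP 10.3 covers the endpoints of that section, not the primary, and does not mention ULT.

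**The concern.** The primary objective (SAP 3.1) concerns the effect of pegloticase on sUA during Month 6 of treatment. The study has one arm, so no control group removes the contribution of another urate-lowering drug. Take a subject who stops for an adverse event, restarts allopurinol or febuxostat after the End-of-Pegloticase visit, and has sUA below 6 mg/dL at Weeks 20 to 24. On the visible text this is a pegloticase responder.

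At stake are the estimated response rate, its exact lower bound, and the reading in protocol 9.6.9 that 14 of 20 responders places the rate above 43.5%. Protocol 9.6.5 plans no formal test, so this is a matter of estimation and interpretation, not of a type I error claim. Stopping-rule subjects and COVID-19 disruptions are already dealt with in the primary analysis and are not part of the point.

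**Working it through.** **1. Reproduce the plan's figure.** Inputs: n = 20, threshold 14/20, benchmark 43.5%, stated lower bound of about 46% (protocol 9.6.9); two-sided 95% Clopper-Pearson interval (SAP 10.2). The lower bound is the 2.5% quantile of Beta(x, n − x + 1).

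| Responders | Rate | Lower bound |
|---|---|---|
| 13/20 | 65% | 40.8% |
| 14/20 | 70% | 45.7% |
| 15/20 | 75% | 50.9% |

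14/20 reproduces the stated 46%, and 14 is the smallest count whose bound exceeds 43.5%.

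**2. Effect of one ULT-controlled early stopper.** 1/20 = 5 points. Removing one takes 14 to 13 (45.7% to 40.8%, now below 43.5%), or 15 to 14 (50.9% to 45.7%, still above). One subject therefore changes the reading only at exactly 14. The 5 points hold only at n = 20: COVID-19 exclusions (SAP 10.2) or replacements (protocol 9.3.4.1) can change the denominator.

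**3. Chance of exactly 14/20.** The documents give no expected scored rate p, so a range is assumed. P(X = 14) = C(20,14) p^14 (1 − p)^6 = 3.7% at p = 0.5, 12.4% at 0.6, 19.2% at 0.7 and 10.9% at 0.8. A changed reading also needs an affected subject among those 14, so its chance is lower than these figures.

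**4. How much of Month 6 ULT could cover.** SAP 8.4, Table 1 puts Week 20 at Day 141 and Week 24 at Day 169: 169 − 141 = 28 days.
- Last infusion at Week 18 or earlier: the End-of-Pegloticase visit is due by Week 20, so ULT can cover essentially all 28 days. If that visit is at Week 20, the Week 20 sample itself precedes ULT.
- Last infusion at Week 20, visit at Week 22 (Day 155): 169 − 155 = 14 of 28 days.

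These are possibilities, not probabilities.

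**5. How many subjects.** The documents contain no forecast. Rough markers, all from protocol 7.1.2, count stoppers and not ULT-controlled responders:
- Anaphylaxis at 6.5%: 0.065 × 20 = 1.3 per 20, before overlap with the stopping rule.
- Assuming it falls in the 26% to 8% ratio given for infusion reactions under the stopping rule: 0.065 × 8/26 × 20 = 0.4.
- Assuming only the 2 of 22 first reactions not preceded by sUA above 6 mg/dL count: 0.065 × 2/22 × 20 = 0.12.
- In the cited trial with 7 kidney transplant recipients, two stopped. One had a pancreatic graft and would be ineligible here. The other was the only recipient with anti-pegloticase antibodies and might have met the stopping rule. That leaves 0 or 1 of 6 (95% CI 0 to 45.9%, or 0.4 to 64.1%), too few to forecast from.

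The share of such stoppers who would be below 6 mg/dL on ULT is not given, and none is assumed.

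**6. Passages that do not agree.**
- The synopsis fails a subject with "sUA level >6 mg/dL at 2 consecutive study visits beginning with the Week 2 Visit through Week 24", not limited to pre-infusion samples. Protocol 9.6.5.1 applies "if the subject had 2 pre-infusion sUA levels" above 6 mg/dL. An early stopper who rebounds before ULT acts may fail under the first and not under the second.
- The synopsis ("will be considered a non-responder if sUA values are not collected at the planned time points") and protocol 9.6.5.1 fail withdrawals with uncollected values. SAP 10.2 lets a single Month 6 value decide.
- Protocol 9.4.1 mentions resuming ULT only after Week 24. Protocol 9.1 and 9.3.3.1.1 allow it after the End-of-Pegloticase visit.

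**The case against.** **Redaction.** Four blacked-out blocks in SAP 10.2 come directly before the quoted sentence. The protocol rule on uncollected values is absent from the visible SAP text, and SAP section 14 does not list it as dropped, so those blocks may hold handling rules for this very group. This stands, and limits confidence to medium. A reader might infer that no ULT rule can exist because the SAP calls the stopping rule the only exception. That does not follow: the next paragraph adds a COVID-19 exception, so the sentence is not exhaustive.

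**Deliberate choice.** Both documents score off-drug values, and the protocol goes out of its way to collect them. An all-observed approach is legitimate, but nothing visible says that ULT control is meant to count, and no visible analysis shows its effect. So the approach may stay as primary, with its effect shown.

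**Few subjects.** Eligibility (protocol 9.3.1) requires failure of, intolerance to or contraindication to conventional ULT, and sUA rose above 6 mg/dL before the first infusion reaction in 20 of 22 subjects. Both make a ULT-controlled early stopper uncommon, though not impossible. This stands and sets the size of the point. A reader might infer a serious risk of false success: with a true rate of 43.5%, the chance of 14 or more of 20 is 0.015, and it reaches 0.363 if 20% of subjects are such stoppers and all are controlled on ULT. Nothing in the documents supports those inputs.

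**The remedy has its own bias.** Failing everyone who took ULT also fails a Week 20 stopper with remaining pegloticase effect, and one who took only a short course. True, which is why the all-observed result should be kept beside it.

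**Loose wording.** Protocol 9.4.1 may be an incomplete restatement, and the synopsis may be shorthand. Perhaps so, but each difference can change who is scored a responder or when ULT is taken to begin.

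**Conclusion.** The point holds on the visible text, at modest size and medium confidence. ULT control can be credited to pegloticase in the primary and the <5 mg/dL endpoint for subjects who stop early for reasons other than the stopping rule or COVID-19. Compared with scoring them as non-responders, this can only raise the rate and its lower bound. The number affected is unknown and probably zero or one. The 43.5% reading changes through one subject only if that subject is among exactly 14 of 20 responders. The verdict assumes that the redacted blocks contain no ULT rule and that the denominator is 20. It does not support a claim that the study's conclusion is likely to be wrong. It supports making the handling of ULT explicit.

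**What to change.** - In SAP 10.2, and through it 10.3.1, score as non-responders those subjects who stopped pegloticase before the Week 22 infusion and then took oral ULT (protocol 9.4.10) before or during their Month 6 samples. Keep the present all-observed rule as a sensitivity analysis.
- If the sponsor prefers the all-observed rule as primary, pre-specify the ULT-as-non-response analysis as the sensitivity analysis.
- Either way, report the number of Month 6 responders off pegloticase with and without ULT, and apply the same ULT handling in sensitivity analysis (1).
- Leave the COVID-19 rule and subjects who received the Week 22 infusion unchanged. Record any change in SAP section 14.
- If a redacted block already covers ULT, confirm that it does; only the count is then needed.
- Separately, reconcile the synopsis with protocol 9.6.5.1 (which sUA values trigger non-response), protocol 9.6.5.1 with SAP 10.2 (uncollected values against the single-value rule), and protocol 9.4.1 with 9.1 and 9.3.3.1.1 (when ULT may resume). Which clinical rule applies is for the sponsor to decide.

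Cost: SAP wording only. Protocol 9.4.9 already records start and stop dates of medications, and SAP 9.4.2 already tabulates gout medications started after the last infusion. The response rate may come out slightly lower.

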#### **Duration of Treatment and Follow-up:**

**Screening:** Up to 35 days prior to the Day 1 visit

**Treatment Period:** Pegloticase for 24 weeks (infusion visits every 2 weeks from Day 1 until the Week 22 Visit).

**End-of-Pegloticase-Infusion Visit (if applicable):** If the subject discontinues pegloticase treatment prior to the Week 22 infusion, such as due to the sUA stopping rules, the subject will complete this visit within approximately 2 weeks of the last infusion. Subjects will continue in the study.

**End-of-Study/Early Termination Visit:** Subjects who discontinue treatment during the 24-week treatment period study will be encouraged to continue study participation through the Week 24/End-of-Study Visit. Subjects who discontinue treatment prior to the Week 24 Visit and are not willing to continue in the study will complete the Early Termination Visit.

**Safety Follow-up Visit:** All subjects will receive a safety follow-up phone call/email approximately 30 days after the last dose of pegloticase to assess if any AEs/SAEs have occurred and will return to the clinic for a follow up visit 3 months after the last pegloticase infusion.

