##### **9.3.3.1.1 Study considerations for subjects ending pegloticase infusions prior to 24 weeks**

- All subjects will remain on study through Week 24 regardless of whether they stop infusions due to sUA stopping rules or other reason (e.g., withdrawal of consent for pegloticase infusions).
- Subjects are encouraged to continue to participate in all visits through the end of the study. Subjects are especially encouraged to complete study visits at the study site during key efficacy and safety collections at Weeks 20, 21, 22, 23, and 24 so that sUA labs and other key assessments can be completed. During visits between these key efficacy and safety collection visits, in subjects who have stopped infusions, subjects may complete study visits

in person or via telephone to collect AEs, concomitant medications and gout flare information.

- Activities related to pre/post infusion monitoring or medication dispensation will not be completed once a subject has stopped pegloticase infusions. These activities include:
  - Infusion reaction prophylaxis;
  - IR prophylaxis compliance;
  - Pegloticase infusion; and
  - Pegloticase PK sampling
- Re-introduction of oral ULTs should not start until after the End of Pegloticase Visit laboratory tests are collected.

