#### 9.3.3.2 Removal of Subjects From Study

In addition to completion of therapy and designated study visits through Week 24, the reason for discontinuation from the study should be recorded on the eCRF using 1 of the following categories:

- Lost to Follow-up: The subject does not return to the clinic for scheduled assessments, and does not respond to the site's attempts to contact the subject;
- Withdrawal by subject: The subject withdraws from the study. The clinical site should attempt to determine the underlying reason for the withdrawal and document it on the eCRF (i.e., voluntary withdraw, relocation, lack of transportation, etc.). The underlying reason should be specified;
- Study Terminated by Sponsor: The Sponsor, IRB, or regulatory agency terminates the study; and
- Death

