#### 9.5.7.4 Week 24/End-of-Study/Early Termination Visit

- [REDACTED]
- Investigator review of clinical status and subject treatment goals;
- Perform a targeted physical examination (at a minimum this should include heart, lungs and abdomen).
- Record vital signs (BP, respiratory rate, temperature, and heart rate) prior to the pegloticase infusion and any time after the end of the infusion, but prior to discharge (see Section 9.5.4.4). [REDACTED]  
[REDACTED]  
[REDACTED]  
[REDACTED]  
[REDACTED]
- Record weight;
- Administer HAQ [REDACTED]
- Administer subject self-reported gout flare assessment questionnaire;
- [REDACTED]
- [REDACTED]  
[REDACTED]
- Obtain a urine sample from all females of childbearing potential for performance of a pregnancy test;
- Obtain blood samples for hematology and clinical chemistry analysis;
- Obtain blood and urine samples for allantoin;
- Obtain blood samples for pegloticase PK analysis;
- Obtain blood samples for anti-PEG and anti-uricase IgG antibodies;
- Obtain whole blood and serum samples for potential analyses of biomarkers from consenting subjects;

- Obtain a blood sample (1 sample) for measurement of sUA; and
- If hand held device is provided, perform fingerstick for uric acid measurement;
- Inquire about AEs and concomitant medication use.

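### SAP 10.2 scores subjects who stopped pegloticase early on whatever Month 6 sUA values exist, even one, whereas protocol 9.6.5.1 can score them as non-responders

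*SAP*

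**What the plan says.** **SAP 10.2.** The Month 6 curve is built from observed sUA at Weeks 20, 21, 22, 23 and 24, and missed collections are not imputed. Results from visits without an infusion are used. The one stated exception is a subject who met the stopping rule before Week 24, who is a non-responder. Then: "If only one sUA result is collected during the Month 6 period, response will be based on the single value", the criterion being strictly below 6 mg/dL. COVID-19 disruption has its own paragraph. Four blocks between the no-imputation paragraph and these sentences are redacted.

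**Protocol 9.6.5.1.** A subject who leaves treatment for a reason other than the stopping rule "prior to or during Month 6 will be considered a non-responder if sUA values are not collected at planned timepoints".

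**Protocol synopsis, Criteria for Evaluation.** A similar rule, but not the same one. It covers withdrawal "prior to Month 6 (for the primary endpoint", and it applies to any reason, without the stopping-rule carve-out.

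**Exit samples.** After early cessation of infusions, "the subject will complete this visit within approximately 2 weeks of the last infusion" (synopsis, Duration of Treatment and Follow-up). Subjects who stop treatment and "are not willing to continue in the study will complete the Early Termination Visit". The procedures there (protocol 9.5.7.4) include "Obtain a blood sample (1 sample) for measurement of sUA". SAP 8.4 assigns both kinds of visit to a scheduled visit by study day and uses the data if no scheduled value exists.

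**Retention.** Protocol 9.3.3.1.1 states "All subjects will remain on study through Week 24 regardless" of why infusions stopped, and 9.5.7.3 requires the Week 20 to 24 visits on site. Study exit is still provided for. Protocol 9.3.3.2 lists as a reason: "The subject withdraws from the study".

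**Elsewhere in the SAP.** Section 10.3.1 carries the 10.2 method over to the 5 mg/dL endpoint. Section 14 lists changes to the analysis populations and to safety-endpoint wording only.

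**The concern.** The primary endpoint is meant to show sustained control: sUA below 6 mg/dL for at least 80% of Month 6. A subject who stopped pegloticase for, say, an adverse event and then gave only part of the planned Month 6 samples has not shown that. The protocol deals with this by scoring such a subject as a failure. The visible SAP text deals with it by using what was collected, down to one value. SAP 10.2 itself declines to calculate a proportion of hours from one data point or none, yet it classifies response from one.

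If the SAP is followed as it reads, the primary and the 5 mg/dL response rates may include subjects whom the protocol counts as non-responders, and nothing declares the change. Neither sensitivity analysis would show the difference. The first restores post-discontinuation results for stopping-rule subjects, and the second restores results after COVID-19 disruption. The planned count of subjects with a single below-cutoff value does not separate withdrawn from on-treatment subjects.

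**Working it through.** **1. The rules side by side.** Take a subject who stopped pegloticase for a reason other than the stopping rule or COVID-19, with every observed Month 6 value below 6 mg/dL. Protocol 9.6.5.1 does not say whether any or all planned samples must be missing, so both readings are shown.

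| Observed in Month 6 | SAP 10.2, visible text | Protocol, any missed | Protocol, all missed |
|---|---|---|---|
| All five visits | responder | responder | responder |
| Several visits, not all | responder | non-responder | responder |
| One planned value | responder | non-responder | responder |
| Exit sample(s) only, windowed into Weeks 20-24 | responder | non-responder | non-responder unless the exit sample counts as planned |

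Under the any-missed reading, the conflict covers every incompletely sampled withdrawn subject with some values; the single-value case is the extreme. Under the all-missed reading, only the last row conflicts, and only if an exit sample is not a planned one. An unscheduled sample, which SAP 8.4 also windows, raises the same question.

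**2. Can an exit sample fall in Month 6?** Inputs: SAP Table 1 (Week 18 = Days 121-134, Week 20 = Days 135-144, Week 24 from Day 166), infusion visits within 3 days of target, and the end-of-infusions visit within 14 days.
- Last infusion at Week 16 (Day 113, at latest 116): exit by Day 116 + 14 = 130, which is in the Week 18 window. No overlap.
- Last infusion at Week 18 (Day 127): exit by Day 127 + 14 = 141. Days 135-141 map to Week 20.
- Last infusion at Week 20: pre- and post-infusion samples are both planned, so there are normally two values already.
- Early Termination Visit on Day 135 or later: maps to one of Weeks 20-24 whatever the last infusion.

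A Week 18 stopper who then leaves the study should also give an Early Termination sample, so a single value normally requires the two visits to coincide or the second to be missed.

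**3. Direction.** The protocol rule can only turn a SAP responder into a non-responder. With k such subjects, responders under the SAP = responders under the protocol + k, with k at least 0, and the rates differ by k/N. For k = 1 and N = 20: 1/20 = 5.0 percentage points.

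**4. Scale against the plan's benchmark.** Exact lower 95% bound = Beta quantile(0.025; x, n - x + 1).
- Protocol 9.6.9 states about 46% at 14/20. Quantile(0.025; 14, 7) = 0.4572, so this reproduces.
- 13/20: quantile(0.025; 13, 8) = 0.4078.

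So 14 is the smallest count whose lower bound exceeds 43.5%, and one subject is enough to cross it. COVID-19 exclusions or replacements can change N. Assuming N = 18, the step is 41.0% (12/18) to 46.5% (13/18); assuming N = 22, it is 40.7% (14/22) to 45.1% (15/22).

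**The case against.** The strongest reply is the redaction. A withdrawal rule could well stand where the four blocks are, and SAP 10.2 tabulates subjects with no Month 6 data although no visible sentence scores them outside COVID-19. The visible only-exception sentence concerns the use of results from visits without an infusion, so it is weak evidence that no such rule exists. A reader might infer that the SAP has dropped the protocol rule; the documents do not show that. What can be said is that the single-value sentence carries no qualifier.

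Second, the conflict depends on how protocol 9.6.5.1 is read. If all planned samples must be missing, a withdrawn subject with one planned value is outside the rule and the documents agree. An exit sample may itself be planned: the synopsis schematic makes the Week 24 visit double as the Early Termination Visit, and SAP 8.4 places exit data in the scheduled visit. This stands, and it limits the claim to the conditional form given here.

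Third, the effect may be nil. The protocol keeps subjects on study and requires the Month 6 visits, protocol 9.6.5 plans no formal testing, and SAP 10.2 already counts single-value subjects. All true. But study exit is allowed, the count mixes withdrawn and treated subjects, and it misses withdrawn subjects with two or more values.

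**Conclusion.** The point holds as a conditional conflict that should be fixed, with medium confidence. On the visible text, following SAP 10.2 can give a different primary classification from protocol 9.6.5.1 for subjects who stopped treatment for reasons other than the stopping rule or COVID-19. The difference is only ever in the favourable direction. How wide it is depends on two things that the documents leave open: whether any or all planned samples must be missing, and whether a windowed exit sample counts as planned. It also assumes that no redacted block already holds the rule.

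The number affected is unknown and may be zero. The move from 40.8% to 45.7% might be read as the bias from this rule, but the documents do not support that: it is what any one subject does at N = 20. Nor would a formal test be overturned, since none is planned. The 14/20 figure in protocol 9.6.9 is still the benchmark against which the result will be read, and scoring should not differ between the two documents so close to it.

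**What to change.** In SAP 10.2, for both the 6 and 5 mg/dL analyses:
- Apply the protocol rule before the observed-value and single-value rules. Suggested text: a subject who withdraws from study treatment prior to or during Month 6, for a reason other than the stopping rule or COVID-19, is a non-responder if any planned Month 6 sUA visit (Weeks 20 to 24) has no value; a windowed End-of-Pegloticase or Early Termination sample does not by itself satisfy this. The trigger (any missed visit) and the treatment of exit samples settle points that the protocol leaves open, so the sponsor should confirm them. COVID-19 cases stay under their existing paragraph.
- Limit the single-value rule to subjects who have not withdrawn from treatment.
- Keep the current observed-value scoring as a labelled sensitivity analysis, and split the single-value counts by treatment status.

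If the sponsor intends observed-value scoring as primary, declare it in section 14 and make the protocol-rule version the sensitivity analysis. If a redacted block already holds the rule, cross-refer the single-value sentence to it. Align the synopsis with protocol 9.6.5.1 on timing and on the stopping-rule carve-out.

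Cost: a few sentences and one programming flag, with no new data. The reported response rate may be slightly less favourable.
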